#### **Short Description**

General anesthesia often reduces blood pressure whereby blood flow to the brain and other vital organs may become insufficient. Thus, medicine is often administered to maintain blood pressure but it is unclear at what level blood pressure should be aimed at during anesthesia.

Thirty patients undergoing major abdominal surgery will be included. The study will start one hour after the start of surgery and lasts for approximately half an hour. The purpose of the study is to evaluate whether blood flow to the brain can be increased by maintaining blood pressure at a higher level than that used in clinical practice. In the study, MAP is adjusted to a high, moderate, and low level for a short time. The low level of blood pressure used in the study, corresponds to the level aimed at in clinical practice. The drug noradrenaline will be used to control blood pressure. Blood flow to the brain will be evaluated on the neck using ultrasound.

#### Background

Propofol anesthesia reduces cerebral blood flow (CBF) and mean arterial pressure (MAP) but it is unclear whether the decrease in CBF is accentuated by hypotension. Cerebral autoregulation is generally considered to maintain CBF when MAP is between 60-150 mmHg. Hence, vasoactive medication is administered if MAP decreases to below approximately 60 mmHg.

It is controversial whether there is a plateau for cerebral autoregulation. Thus, middle cerebral artery blood velocity (MCA Vmean), as an index of CBF, is associated to MAP during pharmacological changes in MAP between approximately 40-125 mmHg. Similarly, CBF is affected by pharmacological changes in MAP between 40-80 mmHg during hypothermic cardiopulmonary bypass surgery in propofol anesthesia. Arterial hypertension may increase the lower limit of cerebral autoregulation which can be mitigated by antihypertensive treatment.

Cognitive dysfunction and delirium are common following major surgery, particularly in the elderly, and may be related to hypotension and cerebral hypoperfusion. Further, hypotensive anesthesia is associated with an increase in markers of neuronal damage, but studies have been too small to detect any difference in incidence of cognitive dysfunction following hypotensive as compared to normotensive anesthesia.

In young healthy adults, propofol anesthesia causes limited reduction in blood pressure and decreases CBF by approximately 50% by a reduction in neuronal activity. An increase in MAP from approximately 80 to 100 mmHg during propofol anesthesia does not affect CBF but it is unknown whether CBF can be increased by an increase in MAP from approximately 60 to 80 mmHg. Propofol appears to maintain cerebral autoregulation but it is unknown whether the lower level of cerebral autoregulation is affected. The internal carotid artery supplies most of CBF and dilates during moderate hypotension with maintained blood flow which indicates that the vessel contributes to cerebral autoregulation. Further, central blood volume and cardiac output may be important factors for maintaining CBF.

The study will include thirty patients planned for major abdominal surgery in propofolremifentanil anesthesia combined with epidural analgesia. Internal carotid artery blood flow will be evaluated on the neck using duplex ultrasound. The study will be conducted one hour after the start of surgery and lasts for approximately half an hour. In the study, MAP is set pharmacologically at 80-85, 70-75 and 60-65 mmHg for a short time in random order. The level of 60-65 mmHg corresponds to the level at which MAP is maintained in clinical practice. Control of MAP is by intravenous infusion of noradrenaline, an  $\alpha$  - and  $\beta$  -adrenergic agonist.

## Objective

The purpose of the study is to evaluate whether internal carotid artery blood flow is increased by maintaining MAP at a higher level than that used in clinical practice during propofol anesthesia. Further, we evaluate whether a lower limit of cerebral autoregulation can be detected by comparing the slopes of linear regression of internal carotid artery blood flow and MAP at the evaluations when MAP is 60-65 and 70-75 mmHg and when MAP is 70-75 and 80-85 mmHg.

## Hypotheses

- Internal carotid artery blood flow is higher when MAP is 80-85 mmHg as compared to a MAP of 60-65 mmHg.
- Internal carotid artery blood flow is higher when MAP is 70-75 mmHg as compared to a MAP of 60-65 mmHg.
- Internal carotid artery blood flow is higher when MAP is 80-85 mmHg as compared to a MAP of 70-75 mmHg.
- The slope of linear regression between changes in MAP and internal carotid artery blood flow is higher for the evaluations at a MAP of 70-75 and 60-65 mmHg than for the evaluations at a MAP of 80-85 and 70-75 mmHg.

#### Methods

The study is a single-center, prospective cohort study of thirty consecutive patients planned for major abdominal surgery in propofol anesthesia. In case surgery is cancelled, or if gas anesthesia is used the patient will be excluded and excluded patients will be replaced. The number of dropouts is expected to be between zero to five patients. Patients will be recruited the day before surgery, at which time the internal carotid artery will be evaluated using ultrasound. In case the vessel cannot be visualized, e.g. due to high localization of the carotid bifurcation the patient will not be able to participate in the study.

Anesthesia and surgery are according to clinical practice. Anesthesia is induced by propofol and maintained by propofol and remifentanil. A thoracic epidural catheter is placed at Th8/9 or Th9/10 and epidural anesthesia is initiated before surgery by bupivacaine infusion 0.5%, 5 ml/hr. and bolus 15 mg bupivacaine that is repeated hourly. Stroke volume is optimized after induction of anesthesia by repeated administration of 250 ml 5% human albumin until the increase in stroke volume is less than 10%, and volume optimization is repeated in case of persistent decrease in stroke volume by more than 10%. Noradrenaline infusion (0.6  $\mu$  g/kg\*ml) is started after induction of anesthesia to maintain MAP > 60 mmHg and to avoid volume optimization when the circulation is dilated.

Development of a so-called mesenteric traction syndrome can affect MAP in the first hour of major abdominal surgery. Thus, the study is conducted from 60 min after incision and lasts for approximately half an hour. Anesthesia reduces MAP, but the reduction varies between patients and is affected by administration of propofol, remifentanil, and epidural anesthesia, fluid status, and surgical stimulation etc. The start of the study is postponed until any larger bleeding, transfusion or volume optimization is treated or finished. Before the start of the study, the infusion speed of propofol and remifentanil must have been constant for at least 10 min, and at least 15 min must have elapsed since the last bolus dose bupivacaine, as any changes in anesthesia may affect both cerebral and central hemodynamics. In case the infusion of propofol or remifentanil is changed or bolus bupivacaine is administered during the study, the experiment is halted, and the study is restarted when the anesthesia has been stable for 10 min. The experiment can only be restarted once and only data from the last trial with the highest number of evaluations are used.

In the experiment MAP is temporally set to 80-85, 70-75, and 60-65 mmHg by adjusting the infusion of noradrenaline. The order of evaluations is randomized by drawing an envelope just before the start of the experiment. Noradrenaline is short lasting and have no direct effect on CBF. The experiment lasts approximately 30 min until evaluations have been conducted at the three levels of MAP. If MAP does not drop to 60-65 mmHg by halting the infusion of noradrenaline this evaluation is not conducted but we expect that this will be the case in only few patients. In clinical practice noradrenaline is used to maintain MAP > 60 mmHg. The study is not an investigation of medicinal products as noradrenaline is used as a tool to control MAP.

Administration of noradrenaline is by a central venous or large peripheral catheter, using an electronic infusion pump, and infusion speed is adjusted slowly until the level of MAP is reached. Noradrenaline is effective within 1-2 min after administration and the effect lasts only for a few minutes. When MAP has been stable at the desired level for at least 3 min, measurements are conducted during the following 2 min. When the study is finished, control of MAP will be according to clinical practice. We consider that there is no increased risk by a short term increase in MAP to 80-85 mmHg.

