## **Primary Outcome Measure:**

 Change in internal carotid artery blood flow when mean arterial pressure (MAP) is set to 80-85 and 60-65 mmHg

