Statistical plan: The Effect of Blood Pressure on Cerebral Blood Flow During

Propofol Anesthesia

Brief Title: The Effect of Blood Pressure on Cerebral Blood Flow During Propofol Anesthesia

Official Title: The Effect of Blood Pressure on Cerebral Blood Flow During Propofol Anesthesia

Acronym: CA

Clinical trials ID: NCT03309917

Date: December 22 2017

Unique Protocol ID: H-17021598-61256

Statistical plan

Trial size: The minimal clinically important difference in internal carotid artery blood flow between

evaluations at MAP 60-65 and 80-85 mmHg is considered to be 10% as evaluations using near-

infrared spectroscopy indicate that intraoperative cerebral deoxygenation of > 10% associates to

postoperative cognitive dysfunction. A power calculation indicated that at a 5% significance level

and a power of 80% at least 18 patients are required to detect a difference in internal carotid artery

blood flow of 10% corresponding to 19 ml/min assuming a standard deviation for the change of 27

ml/min (unpublished results from the study "Cerebral Blood Flow During Propofol Anaesthesia" NCT02951273). We plan to include 30 patients.

The primary outcome is change in internal carotid artery flow when MAP is set to 60-65 and 80-85 mmHg. Secondary outcomes are 1) change in internal carotid artery flow when MAP is set to 60-65 and 70-75 mmHg, 2) change in internal carotid artery flow when MAP is set to 70-75 and 80-85 mmHg, and 3) the slope of linear regression of MAP and internal carotid artery flow for the evaluations when MAP was 60-65 and 70-75 mmHg as compared to that of the evaluations when MAP was 70-75 and 80-85 mmHg.

Values are averaged over 2 min. The internal carotid artery flow and conductance are corrected for changes in PaCO₂ from the value at the evaluation at MAP 60-65 mmHg using a CO₂ reactivity of 18%/kPa and for the S_cO₂ a correction factor of 4.3%/kPa is used (unpublished results from the study "Cerebral Blood Flow During Propofol Anaesthesia" NCT02951273). Analysis of the time points when MAP was set to 60-65, 70-75, and 80-85 mmHg is by a repeated measure mixed model, fit by restricted maximum likelihood in a structured covariance model with time as a fixed effect (Proc mixed; SAS 9.4, SAS Institute, Cary, NC, USA). Analysis of variables not normally distributed is after logarithmic transformation or by a Friedman test and if the test is significant changes are evaluated using Wilcoxon signed rank sum test.

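### If both runs of a restarted experiment end with two evaluations, the tie-break to the last run can discard a measured 60-65/80-85 primary pair

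*Protocol*

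**What the plan says.** All of the relevant rules on conduct are in the protocol's Methods section.

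- **Order.** "The order of evaluations is randomized by drawing an envelope just before the start of the experiment". Neither document says whether a restart keeps that order or draws a new envelope.
- **Halt.** "In case the infusion of propofol or remifentanil is changed or bolus bupivacaine is administered during the study, the experiment is halted", and the experiment begins again once anesthesia has been stable.
- **Choice of run.** One restart is allowed, and "only data from the last trial with the highest number of evaluations are used".
- **Skipped level.** "If MAP does not drop to 60-65 mmHg by halting the infusion of noradrenaline this evaluation is not conducted". A run can therefore finish without a halt and still hold only 70-75 and 80-85.

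The primary outcome is "Change in internal carotid artery blood flow when mean arterial pressure (MAP) is set to 80-85 and 60-65 mmHg" (protocol, Primary Outcome Measure). The SAP repeats it, does not mention restarts, and analyses the three levels "by a repeated measure mixed model, fit by restricted maximum likelihood in a structured covariance model with time as a fixed effect". It corrects flow for changes in PaCO2 "from the value at the evaluation at MAP 60-65 mmHg".

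**The concern.** The natural reading of the run-choice sentence is that the run with more evaluations wins and the later run wins a tie. The levels measured play no part. Suppose the first run records 60-65 and 80-85 and is then halted, and the restart also ends with two evaluations, one of them 70-75. The restart is used, and a primary pair that was actually measured is set aside.

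Two things are then lost. The patient has no directly observed primary change. If the retained run lacks 60-65, its flow values also have no reference for the SAP's PaCO2 correction, although the discarded run had one.

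**Working it through.** **1. The plan's own sample size.** Inputs from the protocol's Statistics section: difference 19 ml/min, SD of the change 27 ml/min, 5% significance level, 80% power. Sidedness is not stated; two-sided is assumed. For a paired t-test the noncentrality is (19/27) × √n.

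- Normal approximation: n = ((1.960 + 0.842) × 27/19)² = 15.85, so 16.
- Noncentral t: n = 18, power 80.3%. This matches the stated 18.
- Power is 96.1% with 30 complete pairs, 94.8% with 28 and 92.1% with 25.

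**2. When the rule can lose the pair.** There are three levels, so 3! = 6 orders.

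- A run with three evaluations always holds the pair, and a run with one or none never does.
- If the two runs differ in count, the one with more is used. The pair cannot be lost, because a run that holds it has at least two evaluations and only a three-evaluation run can beat it.
- Loss therefore needs exactly two evaluations in each run, with the pair in the first and not in the second.

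**3. Probability given such a tie, with 60-65 reached in the first run if its turn came.** The first two levels are 60-65 and 80-85 in 2 of 6 orders, so P(pair) = 1/3.

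| Restart | Pair discarded |
|---|---|
| New order drawn, 60-65 reachable | 1/3 × 2/3 = 2/9 (8 of 36 combinations) |
| 60-65 not reached in the restart, new order | 12/36 = 1/3 |
| 60-65 not reached in the restart, same order | 2/6 = 1/3 |
| Same order, 60-65 reached | 0 |

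In the first row, the 8 losing combinations are 2 first-run orders × 4 restart orders. In 2 of those 4 restart orders the retained run is 70-75 with 80-85, so the PaCO2 reference is missing in half of these losses. When 60-65 is not reached in the restart, it is missing in all of them.

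**4. Overall size.** The documents give no halt rate. As an assumption, let each run stop after exactly two evaluations with probability p, independently, with a redrawn order. Expected lost pairs among 30 patients = 30 × p² × 2/9.

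| p | Expected lost pairs |
|---|---|
| 10% | 0.07 |
| 20% | 0.27 |
| 30% | 0.6 |
| 50% | 1.7 |

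**5. Cost of one lost pair.** If the whole patient were lost, the standard error would rise by √(30/29) = 1.017, or 1.7%. The mixed model can still use the patient's remaining evaluations, so this is about an upper bound.

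**6. The proposed priority rule.** If the run holding both 60-65 and 80-85 is preferred first, the loss is 0 in every combination above.

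**The case against.** The strongest reply is that the sequence is rare and the consequence slight, and most of it stands.

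- **Rarity.** Bupivacaine boluses are hourly. A restart 10 min after a bolus plus about 30 min of experiment takes 40 min, which ends before the next scheduled one. A second halt would need a change in propofol or remifentanil or an off-schedule bolus. On the other route, a patient who reached 60-65 in the first run must fail to reach it in the restart, and the protocol expects such failure in few patients overall.
- **Partial information.** The SAP's model is not restricted to complete pairs. A reader might infer that the patient drops out of the primary analysis; the SAP does not support that.
- **Reading 22% as a loss rate.** A reader might take 2/9 as the share of patients or of restarts affected. It is conditional on a two-two tie and on a redrawn order, and the documents establish neither.
- **Non-random loss.** A reader might infer that the tie-break biases the primary result, because failure to reach 60-65 depends on the patient's hemodynamic state. That dependence comes mainly from the rule that skips the level in any patient, restarted or not. The tie-break adds only a small increment.
- **The rule has merits.** It is prespecified and does not depend on the flow results.

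What remains is that, in the ties where it matters, the stated rule gives a worse result for the primary outcome than an equally objective alternative. The sentence can also be read as simply taking the last run. On that reading a pair could be discarded more often, for instance when the restart yields a single evaluation.

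**Conclusion.** The point holds as a small, avoidable weakness in a stated rule. Only at a two-two tie can the tie-break discard a measured primary pair: in 2/9 of such ties with a redrawn order and 60-65 reachable, in 1/3 when 60-65 is not reached in the restart, and in none when the order is kept and 60-65 is reached. The overall frequency cannot be derived from the documents and is probably low. The range of 0.07 to 1.7 pairs among 30 rests wholly on the assumed p of 10% to 50%. With 30 patients planned against 18 required, power is not at risk. The documents do not support a claim that counting evaluations is itself harmful, or that the primary analysis is materially biased or underpowered because of this rule.

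**What to change.** In the protocol's Methods, and in the SAP, which is silent on restarts, replace the run-choice sentence with a three-step priority:

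1. Use the run that contains both the 60-65 and the 80-85 evaluation.
2. If both runs or neither do, use the run with more evaluations.
3. If they are still equal, use the last run.

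Report the number of restarts and which run was used for each patient. Stating whether a restart keeps or redraws the order would also help, although the priority works either way.

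The cost is one sentence in each document. It needs no extra measurements, and the choice stays independent of the flow results. There are two downsides. In the ties affected, a 70-75 evaluation is given up, which slightly reduces the data for the secondary contrasts and the slope comparison. A halted run may also be preferred over one that ran to completion without reaching 60-65.

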#### Measurements

Arterial and central venous pressure are determined invasively while stroke volume, cardiac output, and total peripheral resistance are evaluated by modified pulse-contour analysis of the arterial pressure curve (Nexfin, BMEYE, Holland). Cerebral and biceps muscle oxygenation are evaluated using near-infrared spectroscopy (INVOS 5100C, Somanetics, Troy, MI, USA). Depth of anesthesia is assessed by Bispectral Index (BIS Complete Monitoring Systems, Covidien, USA).

Internal carotid artery blood flow is evaluated unilaterally on the neck using duplex ultrasound (Logiq E, GE Medical System, Jiangsu, Kina). Evaluation is in the longitudinal section at least 1.5 cm distal to the carotid bifurcation with the head turned approximately 30° to the contralateral side. In order to limit the influence of ventilation, three recordings of approximately 15-20 s are conducted at each level of MAP and the mean is reported. A frequency of 8-12 MHz is used and gain is set as high as possible while vessel lumen is echo-free. Ultrasonic adjustments are not changed during the study. Diameter is assessed using automatic software to track the vessel wall (Brachial Analyser for Research v. 6, Medical Imaging Applications LLC, Coralville, IA, USA). The angle-corrected time maximum flow velocity (TAVMAX) is evaluated using pulsed-wave Doppler at an angle of insonation  $\leq 60^{\circ}$ . The TAVMAX corresponds to twice the mean blood velocity and blood flow is:  $0.125*60*TAVMAX* \pi *$ diameter^2. Arterial and central venous blood is sampled for blood gas analysis. Internal carotid artery blood flow is corrected for changes in PaCO2 using a factor of 18%/kPa and for the ScO2 a correction factor of 4.3%/kPa is used (unpublished results from the study "Cerebral Blood Flow During Propofol Anaesthesia" NCT02951273).

#### **Statistics**

Trial size: The minimal clinically important difference in internal carotid artery blood flow between evaluations at MAP 60-65 and 80-85 mmHg is considered to be 10% as evaluations using near-infrared spectroscopy indicate that intraoperative cerebral deoxygenation of > 10% associates to postoperative cognitive dysfunction.

A power calculation indicated that at least 18 patients were required to detect a difference in internal carotid artery blood flow of 10% corresponding to 19 ml/min assuming a standard deviation for the change of 27 ml/min (unpublished results from the study "Cerebral Blood Flow During Propofol Anaesthesia" NCT02951273) to obtain a 5% significance level and a power of 80%. We plan to include 30 patients.

# **Inclusion Criteria**

- Patient planned for Whipple's surgery or total pancreatic resection
- Age > 18 years

# **Exclusion Criteria**

- No informed consent
- Alcohol intake  $\geq$  420 g / week
- Beard on the neck
- Visualization of the internal carotid artery not possible, e.g. due to high
- placement of the bifurcation
- Stenosis that obstructs  $\geq 16\%$  of the internal carotid artery
- Cardiac disease, including congestive heart failure (NYHA II-IV),
- myocardial infarction, valvular heart disease or atrial fibrillation
- Neurologic disease considered to affect cerebral blood flow, including
- dementia, epilepsy, and apoplexy

• Intake of moclobemide, isocarboxazid or tricyclic antidepressantsNeurologic disease considered

## **Primary Outcome Measure:**

 Change in internal carotid artery blood flow when mean arterial pressure (MAP) is set to 80-85 and 60-65 mmHg

## **Secondary Outcome Measures:**

- 2. Change in internal carotid artery blood flow when MAP is set to 70-75 and 60-65 mmHg
- 3. Change in internal carotid artery blood flow when MAP is set to 80-85 and 70-75 mmHg
- Comparison of the slope of linear regression of MAP and internal carotid artery blood flow for the evaluations when MAP is set to 80-85 and 70-75 mmHg and that of the evaluations when MAP is set to 70-75 and 60-65 mmHg

Statistical plan: The Effect of Blood Pressure on Cerebral Blood Flow During

Propofol Anesthesia

Brief Title: The Effect of Blood Pressure on Cerebral Blood Flow During Propofol Anesthesia

Official Title: The Effect of Blood Pressure on Cerebral Blood Flow During Propofol Anesthesia

Acronym: CA

Clinical trials ID: NCT03309917

Date: December 22 2017

Unique Protocol ID: H-17021598-61256

Statistical plan

Trial size: The minimal clinically important difference in internal carotid artery blood flow between

evaluations at MAP 60-65 and 80-85 mmHg is considered to be 10% as evaluations using near-

infrared spectroscopy indicate that intraoperative cerebral deoxygenation of > 10% associates to

postoperative cognitive dysfunction. A power calculation indicated that at a 5% significance level

and a power of 80% at least 18 patients are required to detect a difference in internal carotid artery

blood flow of 10% corresponding to 19 ml/min assuming a standard deviation for the change of 27

ml/min (unpublished results from the study "Cerebral Blood Flow During Propofol Anaesthesia" NCT02951273). We plan to include 30 patients.

The primary outcome is change in internal carotid artery flow when MAP is set to 60-65 and 80-85 mmHg. Secondary outcomes are 1) change in internal carotid artery flow when MAP is set to 60-65 and 70-75 mmHg, 2) change in internal carotid artery flow when MAP is set to 70-75 and 80-85 mmHg, and 3) the slope of linear regression of MAP and internal carotid artery flow for the evaluations when MAP was 60-65 and 70-75 mmHg as compared to that of the evaluations when MAP was 70-75 and 80-85 mmHg.

Values are averaged over 2 min. The internal carotid artery flow and conductance are corrected for changes in PaCO₂ from the value at the evaluation at MAP 60-65 mmHg using a CO₂ reactivity of 18%/kPa and for the S_cO₂ a correction factor of 4.3%/kPa is used (unpublished results from the study "Cerebral Blood Flow During Propofol Anaesthesia" NCT02951273). Analysis of the time points when MAP was set to 60-65, 70-75, and 80-85 mmHg is by a repeated measure mixed model, fit by restricted maximum likelihood in a structured covariance model with time as a fixed effect (Proc mixed; SAS 9.4, SAS Institute, Cary, NC, USA). Analysis of variables not normally distributed is after logarithmic transformation or by a Friedman test and if the test is significant changes are evaluated using Wilcoxon signed rank sum test.

Difference in the slope of linear regression of changes in MAP and internal carotid artery flow for the evaluations at MAP 60-65 and 70-75 mmHg as compared to that for the evaluations when MAP was 70-75 and 80-85 mmHg is by a linear mixed model, fit by restricted maximum likelihood. The outcome parameter is relative change in internal carotid artery flow and the fixed effects are change in MAP, a condition factor for the two situations and an interaction factor to indicate a difference in slope. Values are presented as mean \pm SD or median with interquartile range

for not normally distributed data and statistical significance is set at P < 0.05. Figures are drawn in R for Windows (version 3.4.1) using the package ggplot2.

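### Does the CO2 correction break down for patients who have no evaluation at MAP 60-65 mmHg?

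*SAP*

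**What the plan says.** The SAP corrects flow and conductance for PaCO2 changes "from the value at the evaluation at MAP 60-65 mmHg using a" CO2 "reactivity of 18%/kPa", and gives 4.3% per kPa for cerebral oxygenation. The protocol, under Measurements, states the correction without a reference level: "Internal carotid artery blood flow is corrected for changes in" PaCO2, "using a factor of 18%/kPa".

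The protocol, under Methods, allows the reference evaluation to be absent: "If MAP does not drop to 60-65 mmHg by halting the infusion of noradrenaline this evaluation is not conducted". It expects this in only a small number of patients and gives no figure. A second, smaller route to missing levels is a run halted for a change in anaesthesia: "The experiment can only be restarted once and only data from the last trial with the highest number of evaluations are used". The replacement rule covers cancelled surgery and gas anaesthesia, not a missing pressure level.

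Two planned analyses do not themselves need a 60-65 mmHg flow. One is the secondary outcome "Change in internal carotid artery blood flow when MAP is set to 80-85 and 70-75 mmHg". The other is the upper segment of the slope comparison, where the contrast with the "evaluations when MAP was 70-75 and 80-85 mmHg is by a linear mixed model". The three-level comparison is also by a mixed model fitted by restricted maximum likelihood.

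**The concern.** Read literally, the SAP ties the correction to a measurement that the protocol says may not exist. For such a patient the corrected flows at 70-75 and 80-85 mmHg are undefined, although both flows and both PaCO2 values may have been recorded. The analyst could drop the patient, leave the flows uncorrected, or pick another reference, with no written rule for choosing.

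Dropping would lose information from a listed secondary outcome and from the upper slope segment. The loss would not be random: it would fall mainly on patients whose MAP stays above 65 mmHg without noradrenaline. Leaving flows uncorrected would mix corrected and uncorrected values in one analysis. A choice made after seeing the data is something a SAP is meant to prevent.

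**Working it through.** **Inputs from the documents.** Reactivity 18% per kPa (SAP; protocol, Measurements). Target difference 19 ml/min, equal to 10%, so a reference flow of 19/0.10 = 190 ml/min. SD of the change 27 ml/min, 5% significance, 80% power, at least 18 patients required, 30 planned (protocol, Statistics; SAP).

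**Assumptions, because the documents give no values.** Number without the 60-65 evaluation: k = 1, 3 or 5 of 30. PaCO2 of 5.0, 5.2 and 5.4 kPa and flow of 190, 200 and 210 ml/min at the low, middle and high levels.

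**1. The plan's own sample size.** A two-sided paired t-test with difference 19 and SD 27 has power 77.8% at n = 17 and 80.3% at n = 18, so the stated 18 is reproduced. Power is 96.1% at n = 30 and 92.1% at n = 25. Five patients without a primary contrast would therefore leave the primary comparison well above 80%, and the choice of PaCO2 reference cannot restore a contrast they do not have.

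**2. Effect of the reference on the 80-85 v 70-75 change.** The uncorrected ratio is 210/200 = 1.050.

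| Form | Reference | 70-75 flow | 80-85 flow | Ratio | Difference (ml/min) |
|---|---|---|---|---|---|
| Linear | 60-65 | 200/(1 + 0.18 × 0.2) = 193.05 | 210/(1 + 0.18 × 0.4) = 195.90 | 1.0147 | 2.85 |
| Linear | 70-75 | 200 | 210/(1 + 0.18 × 0.2) = 202.70 | 1.0135 | 2.70 |
| Exponential | either | – | – | 1.050 × exp(−0.18 × 0.2) = 1.0129 | – |

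Under the linear form the two references differ by 0.12 percentage points (0.15 ml/min) in that patient. Averaged over 30 patients this is 0.12 × k/30 = 0.004, 0.012 or 0.020 points for k = 1, 3, 5. Under the exponential form the reference cancels from the ratio.

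As a wider check, take a 0.2 kPa difference between the two levels and move the reference up or down by 0.5 kPa. The adjustment to the ratio then runs from −3.2% to −4.0% across the linear forms (dividing or multiplying) and stays at −3.5% for the exponential form.

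**3. Leaving the flows uncorrected.** The ratio would be 1.050 instead of 1.0135, about 3.6 points for that patient. If every affected patient had the same 0.2 kPa drift, the mean would move by 3.6 × k/30 = 0.12, 0.36 or 0.60 points.

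**4. Dropping the flows.** The standard error of the 80-85 v 70-75 change rises by the factor √(30/(30 − k)): 1.017, 1.054 or 1.095 for k = 1, 3, 5.

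**5. Indirect route to the primary estimate.** Moving the reference by 0.3 kPa shifts a flow of 190 ml/min by 190 × 0.18 × 0.3 = 10.3 ml/min. To a first approximation the shift is the same at both of the patient's levels, so it cancels from their own change. It reaches the primary estimate only through the between-patient information in the mixed model. With compound symmetry and known variances, a common shift δ in k patients lacking the 60-65 level moves the 80-85 v 60-65 estimate by (kδ/30) × (1 − ρ)/(1 + ρ), where 1 − ρ = 27²/(2σ²). With an assumed total SD of σ = 40 ml/min, 1 − ρ = 729/3200 = 0.228 and the last factor is 0.228/1.772 = 0.129. For k = 5 the estimate moves by (5 × 10.3/30) × 0.129 = 0.22 ml/min, against a target of 19. With σ = 60 it is 0.09 ml/min.

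**The case for a change.** The strongest case for a change is that the sponsor foresaw the missing evaluation, so the SAP should say what then happens. Omitting the flows, leaving them uncorrected and using another reference are all compatible with the silence. Correcting or not correcting moves an individual ratio by about 3.6 points, where 10% is the difference the sponsor calls important (for 60-65 v 80-85). One sentence would settle it and needs no new data.

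The textual point stands: no section supplies a fallback. The argument from harm is weaker. Leaving flows uncorrected contradicts the stated intention, in both documents, to correct for PaCO2. Dropping these patients is nowhere directed, and the planned mixed models accept patients with two levels. What remains is the choice among references, and step 2 shows that this is nearly neutral. The figures for dropped flows depend on an assumed number of patients and on a reading the plan does not call for.

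A residual ambiguity is whether 18% per kPa is applied linearly or exponentially. It is the only reason the reference affects the ratio at all, and in the worked example the two forms give ratios within 0.2 points of each other (1.0129 to 1.0147).

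**Conclusion.** The concern does not call for a change. The SAP leaves out a detail that an analyst would fill sensibly: with no 60-65 mmHg evaluation, correct for the PaCO2 difference between the two levels the patient has. Correcting a change between two levels for the PaCO2 change between them is the natural reading of the protocol's wording. The effect of choosing one within-patient reference over another is about 0.1 percentage points in an affected patient's 80-85/70-75 ratio under a linear correction, and nil under an exponential one. It is confined to one secondary outcome and one slope segment; the effect on the primary estimate is a fraction of 1 ml/min, and the sample size is unaffected.

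These sizes rest on assumed PaCO2 values, flows and total SD, and on 1 to 5 affected patients, since the documents say only that there will be few. No bias from selective loss can be estimated from the documents. It would matter only if the flows were dropped, which the plan does not ask for. Naming the reference actually used when results are reported would be good practice, but nothing in the design or the analysis turns on it.
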